4.9.7 Demographic and baseline characteristics

Demographic characteristics of the study population will be summarized using descriptive tables including frequencies and proportions. Prevalence of comorbidities studied, and Sars-Cov-2 incidence will be assessed. Demographic data will be presented by type of comorbidity, pre-pandemic and pandemic period (including the different Sars-Cov-2 exposure levels regarding their severity).

[figure not shown]
4.9.8 HZ incidence rates (Descriptive analysis)

[figure not shown]
Incidence rates (number of patients with an incident case of HZ per 1000 persons-years) will be obtained for subjects with and without Sars-Cov-2 in the pandemic period by sex, age-group and comorbidity. HZ incident rates for the pre-pandemic period will be also described by sex, age-group and comorbidity.

The person-time-at-risk (in days) ends at the date of the first event of HZ or the end of follow-up, whichever comes first. Follow-up time will be split according to the time-varying covariates (calendar year, month, week, age and comorbidities). Persons-years will be calculated as the sum of total person-time-at-risk divided by 365.25. Rates 95% confidence intervals will be calculated by the Exact Poisson method.

4.9.9 Secondary objectives

- 1) A statistical analysis like the previous one will be developed to compare the risk of HZ among individuals 18 years and older between SARS-CoV2-free and lab-confirmed.
- 2) The risk of HZ in subjects with Sars-Cov-2 exposed (pandemic) respect to subjects unexposed (pre-pandemic) will be estimated by a multivariate Poisson or negative binomial model according to applicability assumptions. Age, sex and comorbidities will be considered for the adjustment.

3) Describe the likelihood of developing HZ after laboratory-confirmation of SARS-CoV2 according to severity of disease.

We will calculate and compare the predicted probability of developing incident HZ in the 1, 3, 6 months following Sars-Cov-2 (1, 3, 6 – months cumulative incidence) using logistic

regression models. We will compare the overall probability, regarding Sars-Cov-2 severity, and the probabilities obtained from models adjusting for the abovementioned covariates (See section 3.5).

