4.2 Study population and period

The cohort will include all subjects older than 18 years living in Valencia Region, registered in the Regional Health System (RHS) (over 98%) from January 1st 2018 to, at least, December 31st 2020 (or date of data extraction). The inclusion and exclusion criteria will be the following:

Inclusion criteria: Subjects aged 18 years and above covered by the RHS and residing in the Valencia Region during study period.

Exclusion criteria:

- Subjects with less than 12 months of registration to the RHS and subjects with incorrect codification.
- Subjects vaccinated against HZ before the diagnosis of SARS-CoV-2
- Subjects vaccinated against SARS-CoV-2 before the diagnosis of SARS-CoV-2

Start of follow-up: The start of the follow-up is defined as the latest of start of the study (1st January 2018), first date of registration in the database or date of the 18th birthday.

End of follow-up: The end of the follow-up is defined as the earliest of the following cases:

- End of study period
- Loss of follow-up (exit of RHS)
- Exitus
- Vaccination with HZ vaccine
- Vaccination with COVID-19 vaccine
- Development of HZ

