4.6.4 Temporal variables

Temporal variables such as calendar week, month and year will be contemplated to detect trends.

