4.9.4 Number of tests performed in The Region over time

As of December 31st 2020, a total of 2.112.504 SARS-CoV-2 tests were performed. The following table shows the monthly number of positive and negative tests (both PCR and Ag) performed.

			Negative	results		Positive results					
Month	Total tests	Total negatives	% of total	AG	PCR	Total	% of total	AG	PCR		
feb-20	514	468	91,05058366		468	46	9,829059829		46		
mar-20	39403	26394	66,98474735		26394	13009	49,28771691		13009		
abr-20	80998	69783	86,15397911		69783	11215	16,07124944		11215		
may-20	114973	112264	97,64379463		112264	2709	2,413062068		2709		
jun-20	101371	100395	99,03719999		100395	976	0,972159968		976		
jul-20	133709	128809	96,33532522		128809	4900	3,804082013		4900		
ago-20	243498	216819	89,04344184		216819	26679	12,30473344		26679		
sept-20	269026	240845	89,52480429	912	239933	28181	11,74536225	109	28072		
oct-20	305193	255984	83,87610463	11170	244814	49209	20,10056614	4832	44377		
nov-20	394144	323865	82,16920719	44718	279147	70279	25,17634078	14560	55719		
dic-20	429675	348567	81,12340723	67192	281375	81108	28,82558863	20070	61038		
Total 2020	2112504	182/103	86 35216785	123002	1700201	288311	16 957/6562	30571	2/87/0		

4.9.5 Power Calculation for HZ IR comparison among SARS-Cov-2 labconfirmed and SARS-Cov-2 free.

Considering an HZ IR of 7 cases per 1000 persons-year in SARS-Cov-2 free, and the following expected populations: 110 000 SARS-Cov-2 lab-confirmed and 2 000 000 SARS-Cov-2 free, we would be able to find statistically significant (significance level = 0.05) differences in RR for HZ (SARS-Cov-2 free vs. Lab-confirmed) of 10% (RR 1.1) with a power of ~ 80% (power = 0.760864).

Power calculation was estimated based on the Two-sample Poisson Ratio Tests (Different Sizes) from the PASSED package of R (version 4.0.2).

Statistical analysis

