2. TIMELINES

Tasks/Time (months)	ene-21	feb-21	mar-21	abr-21	may-21	iun-21	iul-21	ago-21	sept-21	oct-21	nov-21	dic-21	ene-22	feb-22	mar-22	abr-22	may-22	jun-22	iul-22	ago-22	sept-22
Proposal	***	100-21	1101-2-1	001-21	may-21	jun-2 i	jui-2 i	ugo-2 i	Sopt-21	001-21	1104-21	010-21	0110-22	100-22	11101-22	001-22	may-22	Junezz	101-22	ugo-zz	JOPTEL
Study design and protocol		••																			
and SAP																					
IBR approval			•																		
Contract signature				•																	
Data delivery approval				•																	
Data extraction and collection (5 registries)							•			•			•								
Data cleaning and tabulation																					
Data management and analysis																					
Results interpretation and discusion														•	•						
Primary Objective																•					
Secondary Objectives																	•				
Provisional Report/Review and discusion																			••		
Final Report																				••	
Manuscript Preparation and Submission																					
* Follow Up Meetings																					

3. ANNEX 1

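### Protocol 4.9.9 item 3 estimates 1-, 3- and 6-month HZ probabilities without a common case set or a term for date of positive test, so with follow-up ending near December 2020 the horizons describe differently ascertained cases

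*Protocol*

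**What the plan says.** Protocol 4.9.9, item 3, sets out the severity analysis: "We will calculate and compare the predicted probability of developing incident HZ in the 1, 3, 6 months following Sars-Cov-2". The model is logistic regression, reported overall, by severity and with adjustment. The adjusted results are described as "the probabilities obtained from models adjusting for the abovementioned covariates (See section 3.5". The protocol has no section 3.5: section 3 ends at 3.3, and covariates are in 4.6. The adjusters named for the other models in 4.9.6 and 4.9.9 are age, sex and comorbidities.

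On calendar time, 4.6.4 says only: "Temporal variables such as calendar week, month and year will be contemplated to detect trends". Section 4.9.8 also splits follow-up by calendar year, month and week, for descriptive rates.

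Section 4.4 pools PCR and antigen confirmations. Section 4.2 sets the study period as "from January 1st 2018 to, at least, December 31st 2020 (or date of data extraction" and ends follow-up at, among other events, "Vaccination with COVID-19 vaccine". Under Timelines, the row "Data extraction and collection (5 registries" carries marks in July 2021, October 2021 and January 2022, reading the columns as printed.

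Section 4.9.4 gives the testing history: "The following table shows the monthly number of positive and negative tests (both PCR and Ag) performed". Section 4.9.10 summarises time from diagnosis to HZ by age, sex, frailty, comorbidity and severity, but not by when the person tested positive.

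**The concern.** A logistic model for an event within 6 months needs subjects whose status at 6 months is known. Early in an epidemic, only the earliest cases meet that condition, and those cases were found under different testing from later ones. The 1- and 6-month probabilities can therefore describe largely different people. The step from one horizon to the next then mixes time since infection with who was being tested.

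If subjects with short follow-up were instead kept and counted as free of HZ, the 6-month probability would be pulled down. Item 3 does not say which of these is intended.

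Severity contrasts face a related risk. If the hospitalised share of confirmed cases differed between waves, the hospitalised group has a different calendar mix from the rest. Any difference in HZ rate between waves then enters the contrast. What is at stake is one secondary objective and the exploratory time description, not the primary comparison.

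**Working it through.** **Inputs.** Monthly positives in 2020 from 4.9.4: Feb 46, Mar 13,009, Apr 11,215, May 2,709, Jun 976, Jul 4,900, Aug 26,679, Sep 28,181, Oct 49,209, Nov 70,279, Dec 81,108. Antigen positives: Sep 109, Oct 4,832, Nov 14,560, Dec 20,070.

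**Reproducing the table.** The rows sum to the printed 2,112,504 tests and 288,311 positives, and each month's total equals negatives plus positives. I use counts only. The printed percentage for positives divides by PCR negatives (March: 13,009 / 26,394 = 49.3%, against 13,009 / 39,403 = 33.0% of tests).

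**Testing over time.** Tests in December versus March: 429,675 / 39,403 = 10.9. August versus March: 243,498 / 39,403 = 6.2. Tests per positive: 3.0 in March, 103.9 in June, 5.3 in December. Antigen share of positives: 0% before September, 0.4% in September, 24.7% in December.

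**Who has a complete window if the study ends on 31 December 2020** (whole months):

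| Horizon | Positives to end of | Number | Feb-Jun | Jul-Aug | Sep-Nov | Antigen |
|---|---|---|---|---|---|---|
| 6 months | June | 27,955 | 100% | 0% | 0% | 0% |
| 3 months | September | 87,715 | 31.9% | 36.0% | 32.1% | 0.1% |
| 1 month | November | 207,203 | 13.5% | 15.2% | 71.3% | 9.4% |

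February-May supplies 26,979 positives: 26,979 / 27,955 = 96.5% of the 6-month set and 26,979 / 207,203 = 13.0% of the 1-month set. Only 27,955 / 288,311 = 9.7% of the 2020 positives have a full 6-month window.

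**Moving the study end.** February-June share of the 6-month set (27,955 divided by the eligible positives):

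| Study end | Eligible positives | Feb-Jun share |
|---|---|---|
| 31 Jan 2021 | 32,855 | 85.1% |
| 28 Feb 2021 | 59,534 | 47.0% |
| 31 Mar 2021 | 87,715 | 31.9% |
| 30 Apr 2021 | 136,924 | 20.4% |
| 31 May 2021 | 207,203 | 13.5% |
| 30 Jun 2021 | 288,311 | 9.7% |

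From 30 June 2021 every 2020 positive could reach all three horizons, before vaccination, death or exit. Cases confirmed in 2021 would still enter the shorter horizons first. The protocol gives no monthly counts for them.

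**Severity: an illustration on assumed inputs.** Let s be the February-May share of the set, h the assumed hospitalised share in those months (15% or 40%), 6% the assumed share later, and 1.2 the assumed HZ rate ratio of spring to later cases for reasons other than severity.

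- Spring share among severe: a = s·h / [s·h + (1-s)·0.06]
- Spring share among non-severe: b = s·(1-h) / [s·(1-h) + (1-s)·0.94]
- RR when severity has no effect: (1 + 0.2a) / (1 + 0.2b)

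| Horizon (end 31 Dec 2020) | s | RR, h = 15% | RR, h = 40% |
|---|---|---|---|
| 1 month | 0.130 | 1.03 | 1.08 |
| 3 months | 0.308 | 1.05 | 1.10 |
| 6 months | 0.965 | 1.00 | 1.01 |

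Example (1 month, h = 15%): a = 0.0195 / (0.0195 + 0.0522) = 0.272; b = 0.1107 / (0.1107 + 0.8176) = 0.119; RR = 1.0545 / 1.0238 = 1.03.

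With a rate ratio of 1.1 in place of 1.2, the ranges are 1.02-1.04 at 1 month and 1.02-1.05 at 3 months. If the hospitalised share was the same in all periods, the RR is 1.00. If all 2020 positives are complete at every horizon, s = 26,979 / 288,311 = 0.094 and the 1.2 scenario gives 1.02-1.07, so a later study end does not remove this part.

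**The case against.** The strongest reply is that the end date is not 31 December 2020. That date is a minimum, and the timeline allows a much later cut. This stands. A reader might infer that the 6-month estimate always rests on spring cases, and the protocol does not support that: with an end at 30 June 2021 they are about a tenth of the 2020 positives. However, the end is left open, the imbalance is still large at January 2021, and censoring at COVID-19 vaccination could shorten 2021 windows by an amount the protocol does not let us calculate.

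Second, item 3 is about severity, and a cumulative probability rises with its horizon by construction, so a formal comparison across horizons may not be meant. That is fair. But the three figures will be read side by side, and 4.9.10 has change over time as its subject.

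Third, calendar variables are listed among the covariates and an SAP is planned but not at hand. A reader might infer that the plan excludes period adjustment. It does not; it leaves the matter unclear, through a tentative sentence and a cross-reference to a missing section.

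Fourth, the headline testing figures invite overstatement. Eleven-fold is test volume from the lowest full month, not yield, and volume was already up 6.2-fold by August, before antigen tests. Tests per positive rose only from 3.0 to 5.3 between March and December. Antigen results are 9.4% of the 1-month set, so they are a minor part of the shift.

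Finally, a reader might infer that the severe group is loaded with spring cases and the non-severe group with autumn cases. The protocol gives no hospital or ICU counts by month, so this cannot be shown. Weighting by person-time would also misstate the effect, because a fixed-horizon logistic model counts subjects. At each horizon both severity groups share the same eligible dates, and at 6 months with a December end the distortion nearly vanishes.

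**Conclusion.** The point holds in a conditional form. Item 3 fixes a fixed-horizon binary model without saying who is in each horizon's denominator and without firmly including date of positive test. With an end near 31 December 2020 and complete windows, the 6-month set is 100% February-June and PCR only, while the 1-month set is 71% September-November. Among 2020 positives the imbalance shrinks steadily as the end moves later.

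The shares rest on positive results at all ages (288,311, against 219,144 confirmed persons reported as of January 2021 in 4.9.3), so they approximate, and do not count, adult first infections. The severity effect is a possibility of modest size, a null RR of at most about 1.10 under the assumptions shown, and not a demonstrated bias. This is an inexpensive improvement to a secondary objective and an exploratory one; it does not touch the primary analysis.

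**What to change.** - In 4.9.9 item 3, name period of positive test as a covariate or stratum in the severity models, and correct the reference to section 3.5.
- In the same item, report the 1-, 3- and 6-month probabilities in one common set: cases whose test date allows 6 months before the study end. Alternatively, use a time-to-event method within period of test. Censoring methods alone are not enough, because later intervals would still be informed only by early cases.
- In 4.9.10, add period of positive test to the stratifiers of the time-to-HZ summary.
- Optionally, add a PCR-only sensitivity analysis.

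Test date and test type are already requested from RedMIVA (Annex 1), so no new data are needed. The cost is some wording, slightly wider intervals, and no 6-month estimate for late cases unless follow-up is extended.

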4.4 Sars-Cov-2 exposure

Exposure status of everyone might change within the follow up period (Figure 3): Sars-Cov-2 unexposed in the pre-pandemic period and Sars-Cov-2 exposed in the pandemic period. Sars-Cov-2 exposure levels will be treated as a time-varying variable and the following states will be considered:

- 1) **Sars-Cov-2 unexposed**: subject's follow up period from the start of follow-up to the declaration of the pandemic in Spain (March 14th 2020).
- 2) **Sars-Cov-2 exposed**: subject's follow up period from the start of the pandemic. We will consider the following 2 comparison groups:
 - **Sars-Cov-2 free**: time from the start of pandemic (or the follow-up) to the date of the first Sars-Cov-2 confirmation (by PCR or Ag test). If no Sars-Cov-2 positive test registered, the time period will be until the end of follow-up.
 - **Sars-Cov-2 laboratory-confirmed**: time from the date of the SARS-CoV-2 positive result in RedMiva to the end of follow up.

[figure not shown]

Figure 3. Example of exposure, follow-up and comparisons in the study.

* Subjects with recurrent episodes of Sars-Cov-2 will be treated separately. If the sample size is not large enough for the analysis, these individuals will be excluded for the analysis.

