4.11 Missing data

The Valencia Region databases have a very low percentage (0.02%) of unregistered data; subjects with missing information will be excluded for the study.

Patients with incomplete follow-up will account for the analysis as of the date of loss of follow up.

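### Logistic regression for 1-, 3- and 6-month HZ incidence by severity cannot handle follow-up that stops inside the window, which the protocol's own rules make common

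*Protocol*

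**What the plan says.** The third secondary objective is descriptive: the likelihood of HZ after a confirmed infection, by severity. Section 4.5.2 defines severity by hospitalisation and ICU stay. For the analysis, section 4.9.9, item 3, states: "We will calculate and compare the predicted probability of developing incident HZ in the 1, 3, 6 months following Sars-Cov-2". The quantity and method follow: "1, 3, 6 – months cumulative incidence) using logistic" "regression models. We will compare the overall probability, regarding Sars-Cov-2 severity", together with probabilities from covariate-adjusted models.

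Three other places determine how much of each window is observed:

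- Section 4.4 starts the laboratory-confirmed state at the positive result: "time from the date of the SARS-CoV-2 positive result in RedMiva to the end of follow up".
- Section 4.2 ends follow-up at the first of study end, "Loss of follow-up (exit of RHS"), death, HZ vaccination, "Vaccination with COVID-19 vaccine" or HZ itself. The study period runs "from January 1st 2018 to, at least, December 31st 2020 (or date of data extraction").
- Section 4.11 gives the general rule: "Patients with incomplete follow-up will account for the analysis as of the date of loss of follow up".

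Section 4.9.6 uses a person-time offset (Poisson or negative binomial) and a Cox model for the primary comparison. Item 3 of section 4.9.9 has no counterpart: no restriction to complete windows, no censoring weights and no statement on death.

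**The concern.** A binary logistic model takes a yes or no per subject. Someone who tests positive in mid-November and is censored on 31 December is neither a 3-month case nor a 3-month non-case. The model has no person-time or censoring term, so it cannot carry out the rule in section 4.11.

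The analyst is left with two simple workarounds. Coding censored subjects as non-cases makes the risks too low. Dropping them shrinks the sample and, for the longest window, confines it to one part of the pandemic.

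The severity comparison is also exposed. If the share of severe cases changed over calendar time, severe and non-severe cases would have different lengths of follow-up. Under non-case coding, that difference alone would appear as a difference in HZ risk. Adjusting for age, sex and comorbidities does not restore the missing time.

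**Working it through.** **Inputs.** Positive tests by month in 2020 (section 4.9.4): Feb 46, Mar 13,009, Apr 11,215, May 2,709, Jun 976, Jul 4,900, Aug 26,679, Sep 28,181, Oct 49,209, Nov 70,279, Dec 81,108. HZ rate of 7 per 1000 person-years (section 4.9.5). Minimum study end of 31 December 2020 (section 4.2). The end dates of 31 March and 30 June 2021 are assumptions, used to show the range.

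**Plan's own total.** The eleven months sum to 288,311, which matches the table. October to December contribute 49,209 + 70,279 + 81,108 = 200,596, or 69.6%.

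**Share with a complete window, whole months, study end 31 December 2020.**

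- 1 month (positives to end November): 207,203 / 288,311 = 71.9%
- 3 months (to end September): 87,715 / 288,311 = 30.4%
- 6 months (to end June): 27,955 / 288,311 = 9.7%

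**The same by day.** Positives are spread evenly within each month, with windows of 30, 91 and 182 days:

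| Study end | 30 d | 91 d | 182 d |
|---|---|---|---|
| 31 Dec 2020 | 72.8% | 31.0% | 9.8% |
| 31 Mar 2021 | 100% | 99.1% | 30.4% |
| 30 Jun 2021 | 100% | 100% | 99.1% |

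These shares cover 2020 cases only and count only administrative censoring. Vaccination, exit and death would lower them, and cases arising after 2020 would add new incomplete windows.

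**Workaround 1: censored subjects coded as non-cases.** With constant rate r, window k and available follow-up f, the ratio of the estimate to the true risk is

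mean of [1 − exp(−r·min(k, f))] ÷ [1 − exp(−r·k)].

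Because r is small, this is close to the mean of min(k, f) divided by k, so it hardly depends on r. Counting the day of the result as half a day:

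- 31 Dec 2020, 30 d: 25.9 / 30 = 0.86
- 31 Dec 2020, 91 d: 56.3 / 91 = 0.62
- 31 Dec 2020, 182 d: 72.3 / 182 = 0.40
- 31 Mar 2021, 182 d: 146.6 / 182 = 0.81 (0.80 if that half day is not counted)

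In absolute terms, at 7 per 1000 person-years the true 6-month risk is 1 − exp(−0.007 × 182 / 365.25) = 3.48 per 1000. The estimate at the minimum end date would be about 1.39 per 1000.

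**Workaround 2: complete windows only, study end 31 December 2020.** By whole months, the 6-month analysis keeps 27,955 positives. Of these, 46 + 13,009 + 11,215 + 2,709 = 26,979 (97%) are from February to May. The 3-month analysis is different: of 87,715 positives, 4,900 + 26,679 + 28,181 = 59,760 (68%) are from July to September and 26,979 (31%) from February to May.

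**Quality of the proxy.** The table counts tests at all ages, whereas section 4.9.3 reports 219,144 confirmed cases. Dropping positives before 14 March (even spread within March) moves the 91- and 182-day shares to about 30% and 8%.

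**The case against.** The strongest reply is that 31 December 2020 is only the earliest permitted end. The protocol allows the period to run to data extraction, and its timetable continues into 2022. With an end of 30 June 2021, nearly all 2020 cases have six months of potential follow-up. This stands: 31%, 10% and 0.40 are one end of a range and should not be read as the expected result. It does not remove the problem, because no later date is fixed, newer cases would be truncated in turn, and COVID-19 vaccination also ends follow-up.

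Second, the protocol never says that censored subjects become non-cases, and an SAP may define the denominators. This also stands, so the ratios are conditional on that coding. But the protocol does name the model, and that model as written cannot follow section 4.11.

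Third, a reader might infer that early deaths make the logistic risk in severe cases wrong. The documents do not support this. A subject who dies without HZ and is coded as a non-case is treated as in a cumulative incidence with death competing, so a lower risk from early death is no error against that estimator. The only mortality figure is 6,911 / 381,919 = 1.8% overall (section 1), with none by severity. What is missing is a statement of how death is handled.

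Fourth, a reader might infer that restriction to complete windows always leaves mainly spring 2020 cases. The monthly counts show this for the 6-month window only.

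**Conclusion.** The point holds as a mismatch between a named method and the protocol's own follow-up rules. It should be fixed, but it is not critical: the objective is secondary and descriptive, and the primary analysis already uses methods that handle censoring.

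The size depends on the end date and on how incomplete windows are handled. Complete 6-month windows range from about 10% (31 December 2020) through 30% (31 March 2021) to 99% (30 June 2021) of 2020 cases, before other censoring. With non-case coding and a constant rate, the 6-month risk is about 40% of its true value at the first date and about 80% at the second. The shares are approximate because they rest on positive tests at all ages.

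The severity contrast can be biased if severity is related to calendar time. Neither the size nor the net direction can be given, since the documents contain no hospitalised or ICU shares by month.

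**What to change.** In section 4.9.9, item 3, replace the logistic models with time-to-event estimates starting at the positive result:

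- Aalen-Johansen cumulative incidence of HZ at 1, 3 and 6 months by severity, with death as a competing event and the other exits (study end, leaving the health system, either vaccination) censored.
- A comparison of severity groups by cause-specific Cox regression, or by Poisson regression on split follow-up time, with the covariates already planned.
- Numbers at risk at 1, 3 and 6 months for each severity group.

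State that the same method applies whatever end date is chosen. This brings item 3 into line with sections 4.9.6 and 4.11. The cost is protocol or SAP wording: dates of test result, death, cessation and hospital admission are already in Annex 1, and vaccination dates are already needed to apply the end-of-follow-up rules in section 4.2.
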